The current study is designed to evaluate whether CRS-207 with pembrolizumab effectively primes specific immune responses and results in clinical benefit for patients with previously treated gastric, GEJ, or esophageal adenocarcinoma. It is hypothesized the expansion of tumor-specific T cells in context of blocking the PD-1/PD-L1 pathway may ultimately provide enhanced anti-tumor efficacy. Although there are no precedent data on the safety of CRS-207/pembrolizumab, CRS-207 is currently being evaluated with the PD-1 inhibitor, nivolumab in an investigator-sponsored Phase 2 study (ADU-CL-06; NCT02243371). The study is evaluating survival, safety and immune response following treatment with CRS-207/GVAX pancreas/cyclophosphamide with or without nivolumab in subjects with previously-treated pancreatic cancer. Initial data from this ongoing clinical study suggests an acceptable tolerability profile of both agents at full dose (nivolumab at 3 mg/kg on Day 1 and CRS-207 1×10^9 CFU on Day 2). These data suggest that a dose escalation phase 1 component in the current study is not required.

For the first cycle, pembrolizumab and CRS-207 will be dosed on consecutive days (pembrolizumab on Day 1 and CRS-207 on Day 2). If Cycle 1 is well tolerated, dosing of both agents will occur on the same day (Day 1) for subsequent cycles. Based on prior clinical experience and expected infusion reactions, it is anticipated that the same-day regimen will be tolerated and more convenient for patients. A Safety Run-in is planned to monitor safety for the first 6 subjects.

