6.5.6 Safety Analyses

AEs will be coded according to the Medical Dictionary for Regulatory Activities (MedDRA) version 18.1 or higher and assessed for severity using the NCI-CTCAE v. 4.03. The number and percentage of subjects experiencing any TEAE, overall, and by system organ class and preferred term will be tabulated. The incidence rates adjusted by cumulative exposure will also be presented overall and by cycle. AEs associated with clinical laboratory parameters will be characterized according to NCI CTCAE, Version 4.03. Shifts in toxicity grades from baseline to each visit will be summarized.

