4.2. Evaluation of Subgroups

Subgroup analyses are not planned to be performed for the final analysis.

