10.1. Adverse Events

AEs will be recorded from the time of first study drug administration until 28 days after the last dose of study drug or until a subject initiates a new cancer therapy, whichever is earlier. AEs will also be assessed for severity using the NCI-CTCAE v. 4.03, relationship to each therapy (Definitely Related, Probably Related, Possibly Related, Unlikely Related, Not Related), and seriousness (Yes, No). AEs will be considered treatment-emergent if their onset occurs within the on-therapy period. Summary of events related to any study treatment will be provided.

Sponsor: Aduro Biotech, Inc.
Protocol Number: ADU-CL-14
Version and Date: Version 1.0, 13Mar2018

An overview of treatment-emergent AEs (TEAEs) will be produced, including counts and percentages of subjects with any incidences of: TEAEs, CTCAE Grade 3 or higher TEAEs, TEAEs related to study treatment, CTCAE Grade 3 or higher TEAEs related to study treatment, serious adverse events (SAEs), TEAEs leading to study drug discontinuation, infusion-related reactions (IRRs), and fatal TEAEs.

A separate overview of AEs identified as IRRs related to CRS-207 will be provided. This display will include the number of infusions received by subjects, the number of subjects having an IRR, total number of IRRs per subject, maximum IRR grade, and dose modifications resulting from IRRs.

Adverse events will be coded based on the Medical Dictionary for Regulatory Affairs (MedDRA) for reporting by system organ class (SOC) and preferred term (PT) in descending order of overall incidence. For these summaries, subjects with multiple AEs with the same SOC and/or PT will only be counted once at each level of summarization.

Summaries of adverse events by SOC and PT will include the following types:

- TEAEs;
- TEAEs related to any study treatment (Definitely Related, Probably Related, or Possibly Related);
- CTCAE Grade 3 or higher TEAEs;
- CTCAE Grade 3 or higher TEAEs related to any study treatment;
- CRS-207 infusion-related reactions;
- SAEs.

To account for potential differences in the extent of exposure between the treatment categories, a subject-year adjusted rate will also be presented. The rate is calculated as the number of subjects with an event divided by the total subject-years of safety observation, where subject-years of safety observation for each subject is defined as duration of safety observation (defined in Section 5.3) in days divided by 365.25.

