11. CHANGES TO THE PLANNED ANALYSIS

All efficacy endpoints will be derived and listed for each subject, but will not be summarized.

Sponsor: Aduro Biotech, Inc.
Protocol Number: ADU-CL-14
Version and Date: Version 1.0, 13Mar2018

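### The protocol commits to exposure-adjusted adverse-event rates by cycle; the SAP plans only one pooled rate and does not declare the change

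*SAP*

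**What the plan says.** Protocol 6.5.6, in a sentence repeated in the synopsis, says of treatment-emergent adverse events (TEAEs): "The incidence rates adjusted by cumulative exposure will also be presented overall and by cycle".

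SAP 10.1 introduces its own rate with "To account for potential differences in the extent of exposure between the treatment categories, a subject-year adjusted rate will also be presented" and defines it so: "The rate is calculated as the number of subjects with an event divided by the total subject-years of safety observation". Under SAP 5.3, the safety observation period runs from first dose to 28 days after last dose. In the summaries by system organ class and preferred term, "subjects with multiple AEs with the same SOC and/or PT will only be counted once at each level of summarization".

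For CRS-207 infusion-related reactions (IRRs), SAP 10.1 plans a separate overview: "This display will include the number of infusions received by subjects, the number of subjects having an IRR, total number of IRRs per subject", together with maximum grade and resulting dose modifications. Neither this overview nor the IRR table by organ class and term is split by cycle or dosing regimen. SAP 4.2 adds: "Subgroup analyses are not planned to be performed for the final analysis".

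SAP Section 1 says that the document gives changes from the study protocol. Section 11, where they belong, has one entry: "All efficacy endpoints will be derived and listed for each subject, but will not be summarized".

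**The concern.** A committed safety analysis has been replaced by a simpler one without being recorded as a change. The reason given for the remaining rate, unequal exposure across treatment categories, does not apply: SAP 5.1 assigns every subject to the combination.

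Cycle matters in this design. Cycle 1 gives the two drugs on consecutive days, same-day dosing may follow if the infusions are tolerated, and CRS-207 moves to every other cycle after Cycle 4 (Protocol 6.1). Protocol 4.3 says of same-day dosing that "it is anticipated that the same-day regimen will be tolerated and more convenient for patients". Protocol 6.1 also states that there is no precedent for CRS-207 with pembrolizumab, and it runs the safety run-in through 7 days after the Cycle 2 dose. A reader of the study report would want to see whether events cluster at the first infusion, at the switch to same-day dosing or later. None of the planned tables shows this.

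**Working it through.** **Comparison of the texts**

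| Item | Protocol (synopsis, 6.5.6) | SAP |
|---|---|---|
| Exposure-adjusted rate, overall | Yes | Yes (10.1) |
| Exposure-adjusted rate, by cycle | Yes | Not in 10.1; no such title in 13.1 |
| IRRs by cycle or regimen | Not promised | Not planned |
| Change declared | n/a | Section 11 gives the efficacy change only |

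The plan states no event rate, so there is no figure to reproduce. The SAP's formula can still be run on assumed data to see what the pooled rate conveys.

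**Inputs**
- From the documents: 3-week cycles (Protocol 6.1); observation days = (last dose + 28) − first dose + 1 (SAP 5.3); rate = subjects with an event ÷ total subject-years, with 365.25 days per year (SAP 10.1).
- Assumed for illustration: 20 subjects, all with the same number of cycles; last dose on Day 1 of the last cycle; 10 subjects with one IRR each.

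**Pooled rate**
- 2 cycles: last dose on Day 22, so 22 + 28 − 1 + 1 = 50 days. 20 × 50 / 365.25 = 2.738 subject-years; 10 / 2.738 = 3.65.
- 4 cycles: last dose on Day 64, 92 days. 20 × 92 / 365.25 = 5.038; 10 / 5.038 = 1.99 (1.985 before rounding).
- 6 cycles: last dose on Day 106, 134 days. 20 × 134 / 365.25 = 7.337; 10 / 7.337 = 1.36.

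The time at which the 10 reactions occur does not enter the formula.

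**Split at the end of Cycle 1 (21 days)**
- Cycle 1 subject-years: 20 × 21 / 365.25 = 1.150. If all 10 react in Cycle 1, the rate is 10 / 1.150 = 8.70.
- Later subject-years: 20 × (50 − 21) / 365.25 = 1.588, 20 × (92 − 21) / 365.25 = 3.888 or 20 × (134 − 21) / 365.25 = 6.188. If all 10 react later, the rates are 6.30, 2.57 or 1.62.

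| Cycles | Pooled (either case) | All in Cycle 1: Cycle 1 / later | All later: Cycle 1 / later |
|---|---|---|---|
| 2 | 3.65 | 8.70 / 0 | 0 / 6.30 |
| 4 | 1.99 | 8.70 / 0 | 0 / 2.57 |
| 6 | 1.36 | 8.70 / 0 | 0 / 1.62 |

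Opposite patterns give the same pooled rate. That rate also falls 2.7-fold (134 / 50) with treatment length alone, for the same 10 reactors. For an event tied to an infusion, it mainly reflects how long subjects stayed on treatment.

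**The case against.** The strongest reply has five parts.

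1. **The comparison is not lost.** SAP Section 4 puts all data into by-subject listings, by default in date order, and SAP 13.2 plans listings for IRRs and for administration of each drug. A reader might infer that reactions under the two dosing schedules cannot be compared at all, but the documents do not support that. Reactions could very probably be assigned to a cycle and regimen by hand, although the listing contents are not specified. The IRR overview also gives infusions and IRRs per subject, so a crude overall per-infusion rate can be derived. This part stands.

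2. **The protocol promised less than it may seem.** It names TEAE incidence by cycle. It does not name IRRs, a per-infusion denominator or a contrast of regimens, and comparing regimens is not a study objective. This stands: those items are additions, not restorations.

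3. **By-cycle tables would not test same-day tolerability.** Same-day dosing depends on having tolerated earlier infusions, subjects may stay on or return to consecutive-day dosing, and Cycle 1 is also the first exposure. First exposure, dropout and selection are all confounded with cycle and regimen. This stands too, and it limits any such table to description.

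4. **The scope was cut for a reason.** This is an abbreviated SAP for a report synopsis, written after CRS-207 development stopped (SAP Sections 1 and 3.5). That may explain the omission but does not declare it. The same SAP declared its efficacy cut.

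5. **The protocol's statistical text is only a guide.** Protocol 6.5 says so and leaves detail to the SAP. That permits a change. It does not excuse leaving the change out of a document that says it gives changes from the protocol.

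**Conclusion.** The point holds as an undeclared departure from a committed safety analysis. The protocol states by-cycle exposure-adjusted rates twice; the SAP drops them, gives a reason for the remaining rate that does not fit the design, and lists no change. The practical loss is that no planned summary shows when TEAEs or IRRs occur, and the pooled rate cannot stand in for one.

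The size is moderate. No efficacy result is affected and the data remain in the listings. The rates worked out above rest on assumed counts and equal treatment length, so they show how the formula behaves and do not predict the trial's results. The finding that the pooled rate carries no timing information does not depend on those counts.

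Two stronger conclusions should not be drawn: that the trial promised a comparison of same-day with consecutive-day dosing, or that restoring the by-cycle rates would settle whether same-day dosing is tolerated.

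**What to change.** - **Restore.** In SAP 10.1 and 13.1, add exposure-adjusted rates for TEAEs and for Grade 3 or higher TEAEs by cycle (1, 2, 3, 4, and 5 or later). Use each subject's time at risk within the cycle as the denominator, and say to which cycle the 28 days after last dose belong.
- **Correct the wording.** Delete the reference to treatment categories.
- **Optional addition, not promised by the protocol.** Tabulate CRS-207 IRRs per infusion given, by cycle and by the regimen actually used. Label the table descriptive only, with a note on first exposure, dropout and selection into same-day dosing.
- **If not restored.** State the omission and its reason in SAP Section 11.

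The cost is two or three descriptive tables from adverse-event and dosing data already collected, or one sentence in Section 11. The drawbacks are small cells in later cycles and the risk of over-reading the regimen split, which the label is meant to limit.

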5.3. Study Day and Duration Variables

Reference date calculations will be defined as the following:

- date of interest – reference date + 1 when the date of interest \geq reference date;
- otherwise, date of interest – reference date.

For instance, study day will be based on the date of first study treatment as the reference would either have a negative value if collected before dosing or a positive value if collected after drug dosing; there will be no study day zero.

Duration of time is dependent on reference dates and will be calculated in a manner similar to that of the reference date calculation, assuming that dates of interest will strictly follow reference dates (e.g. no negative values). For example, duration on study is defined as the end of study date – enrollment date + 1. Duration of treatment is defined as the last date of treatment – first dose date + 1. Duration of the safety observation period is defined as (the last date of treatment

Sponsor: Aduro Biotech, Inc.
Protocol Number: ADU-CL-14
Version and Date: Version 1.0, 13Mar2018

+ 28 days) – first dose date + 1. Subjects still receiving ongoing treatment or participating in study follow up at the time of analysis will use imputed treatment end and end of study dates as described in section 5.6.

Survival, or time-to-event, endpoints such as PFS or OS are followed until first event or censoring. As a result, survival time will be calculated as: event or censoring date – reference date + 1. These are further described in Section 7.

When reporting survival or duration outcomes, the results (in days) above will be converted to an appropriate unit. When reporting in months it will be divided by 30.4375; for reporting in weeks it will be divided by 7; and for reporting in years it will be divided by 365.25.

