5.4. Study Time Periods

Safety reporting will be classified by the following study periods for analysis:

Pre-therapy is defined as the period prior to a subject's first dose of study treatment.

On-therapy is defined as the period between first dose of study treatment and within 28 days following the last dose of study treatment.

Post-therapy is defined as the period of time following the on-therapy period.

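### The subject-year adjusted adverse event rate counts time when no countable event can occur, so it understates common early events relative to a time-at-risk rate

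*SAP*

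**What the plan says.** SAP 10.1 gives the formula for the subject-year adjusted rate: "The rate is calculated as the number of subjects with an event divided by the total subject-years of safety observation". The same section fixes the numerator: "subjects with multiple AEs with the same SOC and/or PT will only be counted once at each level of summarization". A subject therefore adds at most one to any row.

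The denominator comes from SAP 5.3, where a page break splits the definition: "Duration of the safety observation period is defined as (the last date of treatment", then plus "28 days) – first dose date + 1". It has no earlier stopping point for a first event, death or a change of therapy. The on-therapy period in SAP 5.4, which decides what is treatment-emergent, has none either: "On-therapy is defined as the period between first dose of study treatment and within 28 days following the last dose of study treatment".

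SAP 10.1 nevertheless says that AEs are recorded only "until 28 days after the last dose of study drug or until a subject initiates a new cancer therapy, whichever is earlier". Protocol 7.3.1 differs for serious adverse events (SAEs). It collects them for 90 days after treatment stops, or for 28 days if new anticancer therapy starts.

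Protocol 6.5.6 asks for incidence rates that take cumulative exposure into account, alongside numbers and percentages of subjects.

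**The concern.** A rate whose numerator stops at the first event needs a denominator that stops there too. Here the subject's remaining time stays in the denominator although it can add nothing to the numerator. The result is neither a first-event rate nor a rate of all events.

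SAP 5.3 and 10.1 also disagree. For non-serious AEs, 5.3 counts time after new cancer therapy during which 10.1 says nothing is recorded. It also counts time after death.

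Efficacy will only be listed (SAP 7 and 11), so safety is the main outcome still summarized. Protocol 4.1.4 describes the expected CRS-207 reactions as common, immediate and mostly over within 48 hours of infusion, and the first CRS-207 infusion is on Day 2 (protocol Table 6-2). If many first events come early, those are the rows where the formula departs most from a time-at-risk rate. A reader comparing such rates with another study could be misled.

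**Working it through.** The documents give no AE rate, so there is no planned figure to reproduce. The formula is from SAP 5.3 and 10.1. The inputs below are assumptions.

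**Inputs**
- p: share of subjects with the event (assumed, 10% to 80%)
- t: day of first onset (assumed; Day 2 is the first CRS-207 infusion)
- O: observation days per subject, the same for all subjects (assumed). By SAP 5.3, O = (last dose day + 28) − 1 + 1 = last dose day + 28. A last dose on Day 22 (2 cycles) gives 50 days. A last dose on Day 106 (6 cycles) gives 134 days.

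**Formulas, per subject-year**
- SAP rate = p × 365.25 / O
- Time-at-risk rate = p × 365.25 / [p·t + (1 − p)·O]
- Ratio = O / [p·t + (1 − p)·O]

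**Step 1: time after the first event, with t = 2 and O = 90**

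| p | Days at risk per subject | SAP rate | Time-at-risk rate | Ratio |
|---|---|---|---|---|
| 10% | 0.2 + 81 = 81.2 | 0.41 | 0.45 | 1.11 |
| 50% | 1 + 45 = 46 | 2.03 | 3.97 | 1.96 |
| 70% | 1.4 + 27 = 28.4 | 2.84 | 9.00 | 3.17 |
| 80% | 1.6 + 18 = 19.6 | 3.25 | 14.91 | 4.59 |

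Treatment length matters little: at 70% the ratio is 3.05 for 2 cycles and 3.22 for 6.

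**Step 2: later onset, with p = 70% and O = 134**
- Day 2: 134 / (1.4 + 40.2) = 3.22
- Day 22: 134 / (15.4 + 40.2) = 2.41
- Day 90: 134 / (63 + 40.2) = 1.30

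**Step 3: does the rate adjust for exposure?** If every subject reacts on Day 2, the SAP rate is 365.25/50 = 7.31 at 2 cycles and 365.25/134 = 2.73 at 6 cycles. The experience is identical, but the rates differ 2.7-fold through treatment length alone.

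**Step 4: time after death or new therapy.** A subject who dies 10 days after a single Day 1 dose is credited with (1 + 28) − 1 + 1 = 29 days instead of 11. Across the trial, suppose a share q of subjects stops being observable d days after last dose. The denominator is then too large by O / [O − q(28 − d)] − 1:
- q = 20%, d = 7, O = 50: 50/45.8 − 1 = 9.2%
- q = 20%, d = 7, O = 134: 134/129.8 − 1 = 3.2%
- q = 10%, d = 14, O = 134: 134/132.6 − 1 = 1.1%
- Less favorable case, q = 40%, d = 7, O = 50: 50/41.6 − 1 = 20.2%

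**The case against.** The strongest defense is that this is a choice of measure. SAP 10.1 states both parts openly and never calls the result a first-event rate, and a total-time denominator fits the protocol's reference to cumulative exposure. That stands in part: the understatement exists only relative to a time-at-risk rate, and the convention does little harm for rare events. It does not cover time after death, or time after new therapy when non-serious AEs are no longer recorded.

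Second, the comparator has limits. A person-time rate suits a roughly constant hazard, not reactions tied to an infusion. In the table, raising incidence from 50% to 80% (1.6-fold) raises the time-at-risk rate from 3.97 to 14.91 (3.8-fold). This stands: for such reactions the percentage of subjects is easier to interpret.

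Third, the scope for harm is limited. Percentages are reported, CRS-207 infusion-related reactions have their own overview and table, all AEs are listed, and no test or decision depends on this rate. This stands too.

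Stronger readings are tempting. A reader might infer that AE rates in this trial will be understated three- to five-fold. The documents give no incidence or first-onset timing for the combination, and protocol 4.1.4 links reactions to CRS-207 administration without saying that they cluster at the first infusion. A reader might also infer that time should be cut at new therapy in every row. Protocol 7.3.1 keeps collecting SAEs for 28 days after treatment stops. Such an SAE would be treatment-emergent and enter the numerator while its time had been removed, which would bias SAE rows upward.

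**Conclusion.** The point holds as a mismatch between a once-per-subject numerator and a denominator containing time when no countable event can occur. Two effects should be kept apart.

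- **Time after the first event** is the larger effect for common early events. Relative to a time-at-risk rate, the SAP rate is low by about 2-fold at 50% incidence and 3-fold at 70% with Day 2 onset. The factor is 1.3 at 70% with Day 90 onset over six cycles. At 10% incidence or less, the time-at-risk rate is at most about 11% higher.
- **Time after death or new therapy** is not specific to early events. It lowers rates generally and modestly, with a denominator about 1–9% too large if 10–20% of subjects are affected 7–14 days after last dose. The new-therapy part does not apply to SAEs.

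These sizes rest on assumed incidence, onset and frequencies, and on equal observation time for all subjects. Crude counts, percentages and listings are unaffected, so the plan's AE reporting as a whole is not understated. The change is worth making, but no trial conclusion depends on it.

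**What to change.** In SAP 5.3 and 10.1, define time at risk separately for each reported term. It runs from first dose to the earliest of first onset of that term, death, last dose plus 28 days and, for non-serious AEs only, start of new cancer therapy. Divide the number of subjects with the event by the sum of these times.

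For SAE rows, do not cut at new therapy. For rows that mix serious and non-serious AEs, apply one cut-off to both parts of the rate. If time ends at new therapy, events starting later leave that rate's numerator but stay in the counts and percentages.

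The cost is SAP wording and a per-term denominator in the AE programs. No new data are needed: AEs, deaths and subsequent therapies already have listings, and SAP 5.6 has rules for partial dates. The downside is that the denominator differs by row. For infusion-linked reactions, the text should point readers to the percentage of subjects.

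If per-term programming is judged too much for an abbreviated plan, the minimum is to end time at death, reconcile 5.3 with the recording window in 10.1, label the rate as subjects with an event per total subject-years, and state its limitation for common early events.
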